8.10. Health Economics or Medical Resource Utilization and Health Economics

Not applicable.

9. STATISTICAL CONSIDERATIONS

The SAP will be finalized before database lock and includes a more technical and detailed description of the statistical analyses described in this section.

9.1. Statistical Hypothesis

No formal hypothesis will be tested in this phase 2 open-label extension study.

9.2. Analysis Sets

The following analysis sets are defined:

Analysis set	Description
Full analysis set (FAS)	All enrolled subjects in the OLE study.
Safety set	All FAS subjects who have been administered study treatment during the OLE.

9.3. Statistical Analyses

9.3.1. General Considerations

- Data collected will be listed with derived variables. Descriptive statistical methods will be used to analyze safety and efficacy data
- The results of this study will not be used inferentially
- No formal sample size calculation is presented
- Summaries will include the number of observations (n), mean, SE, 90% CI, median, minimum, and maximum for continuous measures
- Summaries will include sample size, frequencies, and percentages for categorical variables
- The baseline value will be the last assessment before the first administration of the study drug in OLE
- All study visits will be recalculated based on actual dates. The rules for calculating the analysis visits will be documented in the SAP
- Rules for imputing partial dates or missing dates will be provided in the SAP
- Exposure to IMP will be summarized
- TEAEs, AESIs, SAEs, and other safety parameters will be summarized
- AEs will be classified using the latest version of the MedDRA classification system
- AEs, AESIs, and SAEs will be listed corresponding to MedDRA SOC and PT

- Multiple occurrences of a single PT in a participant will be counted only once at the maximum severity/grade
- AEs with missing severity or relationship to IMP will be classified as severe and treatment-related, respectively. All AEs will be summarized by relatedness to IMP
- Any AEs leading to death or discontinuation of IMP will also be summarized
- Population PK/PD analysis may be performed based on the PK and PD data and reported separately
- Laboratory parameters, physical examinations, vital sign measurements, ECG data and PK, PD, immunogenicity, and biomarker results will be summarized descriptively

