8.3.4. Protocol-Required Laboratory Tests

- Blood and urine samples will be analyzed at a central laboratory for serum chemistry and hematology, urinalysis, and specialty laboratory parameters
- Refer to Appendix 2 (Section 10.2) for the list of protocol-required laboratory tests to be performed and the SoA (Section 1.3) for the timing
- The investigator must review the laboratory results, document this review, and record any clinically significant changes occurring during the study as an AE. The laboratory results must be retained with source documents
- Abnormal laboratory findings associated with the underlying disease are not considered clinically significant unless judged by the investigator to be more severe than expected for the participant's condition

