9.3.2. Primary Endpoint Analysis

Primary endpoint of long-term safety will be assessed through AEs, AESI, incidence of SAEs, changes in laboratory test results, vital signs, and ECG. Please refer the Section 8.3 for more details. Full details of the secondary analyses will be included in the SAP.

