3.4. Changes to Analysis from Protocol

The Biomarker data will not be analyzed due to the lack of available data to BIOS.

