17.1.2. Laboratory Evaluations

Results from the central laboratory will be included in the reporting of this study for serum chemistry and

Copyright © 2009, 2010, 2012, 2016, 2018, 2019, 2021, 2024 IQVIA. All rights reserved. The contents of this document are confidential and proprietary to IQVIA Holdings Inc. and its subsidiaries. Unauthorized use, disclosure or reproduction is strictly prohibited.

hematology, coagulation, urinalysis, serology (e.g. viral marker testing), and specialty laboratory parameters. A list of laboratory assessments to be included in the outputs is included in [Appendix 2](#) (Table 6) of the protocol. These are mainly as follows.

Laboratory Assessments

Hematology	RBC count, platelet count, hemoglobin, hematocrit, MCV, MCH, %reticulocytes, WBC count with differential: neutrophils, eosinophils, lymphocytes, basophils, monocytes
Serum chemistry	ALT, AST, GGT, alkaline phosphatase, albumin, creatinine, potassium, BUN, CRP, glucose, sodium, total protein, calcium, bilirubin (total and direct)
Routine urinalysis	Specific gravity, pH, glucose, protein, blood, ketones, bilirubin, urobilinogen, nitrite, leukocyte esterase, microscopic examination (if blood or protein is abnormal)
Pregnancy testing	Urine test at baseline and other time points (as needed for WOCBP potential, defined in Section 10.4.1 of the protocol)

^a This result will be blinded baseline and up to the week 4 (day 29) visit.

ALT=alanine aminotransferase; AST=aspartate aminotransferase; BUN=blood urea nitrogen; CRP = C-reactive protein; GGT = gamma-glutamyl transferase; MCH=mean corpuscular hemoglobin; MCV=mean corpuscular volume; RBC=red blood cell; WBC=white blood cell; WOCBP=women of childbearing potential

Normal ranges are available as provided by the central laboratory and results will be presented in standardized units unless specified otherwise. Clinically significant changes occurring during the study are recorded as an AE.

Quantitative laboratory measurements reported as “< X”, i.e. BLQ, or “> X”, i.e. above the upper limit of quantification (ULQ), will be converted to X for the purpose of quantitative summaries, but will be presented as recorded, i.e. as “< X” or “> X” in the listings.

Continuous laboratory parameters will be summarized using descriptive statistics of actual values and changes from baseline at each analysis visit. Categorical parameters will only be listed.

The following summaries will be provided for laboratory data:

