17.2. Other Safety Outcomes

17.2.1. Physical Examination

Brief physical examination will include weight (recorded on eCRF Vital Signs), assessments of gastrointestinal, pulmonary, cardiovascular, and respiratory systems; and general appearance.

All datapoints obtained after informed consent up to 60 days after IMP discontinuation will be considered. Physical examination abnormalities will be listed with the AE's.

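### The SAP only lists categorical laboratory results and physical-examination findings, although Protocol 9.3.1 promises summaries, and SAP 3.4 does not declare the change

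*Protocol*

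**What the plan says.** Protocol 9.3.1 (General Considerations) states: "Laboratory parameters, physical examinations, vital sign measurements, ECG data and PK, PD, immunogenicity, and biomarker results will be summarized descriptively". The same list of rules gives the form such a summary takes for non-numeric data: "Summaries will include sample size, frequencies, and percentages for categorical variables". Protocol 9.3.2 makes laboratory change part of the primary endpoint: "Primary endpoint of long-term safety will be assessed through AEs, AESI, incidence of SAEs, changes in laboratory test results, vital signs, and ECG". Protocol 8.3.4 counts urinalysis among the required laboratory tests: "Blood and urine samples will be analyzed at a central laboratory for serum chemistry and hematology, urinalysis, and specialty laboratory parameters".

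SAP 17.1.2 splits laboratory data by type. For numeric parameters, "Continuous laboratory parameters will be summarized using descriptive statistics of actual values and changes from baseline at each analysis visit". For the rest, "Categorical parameters will only be listed". On physical examination, SAP 17.2.1 says: "Physical examination abnormalities will be listed with the AE's".

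The section reserved for departures from the protocol, SAP 3.4, contains one entry: "The Biomarker data will not be analyzed due to the lack of available data to BIOS".

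**The concern.** The protocol promises a summary and the SAP delivers a listing, for two kinds of data named in the same protocol sentence. The SAP declares a change for a third item in that sentence (biomarkers) but not for these two.

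The laboratory half carries more weight, because laboratory change is a component of the primary endpoint. Routine urinalysis is where categorical laboratory results are most likely to arise. If urine protein or urine blood is reported in categories, a reader of the study report could not see from a table how many participants moved from normal at baseline to abnormal over 48 weeks. Nor would there be a worst-case count or a tabulated split by parent-study arm. Continuous chemistry and haematology parameters get by-visit change tables, and those with limits or grades also get baseline cross-tabulations. Renal involvement is one of the activity domains of this disease, so urine findings are not incidental.

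**Working it through.** The plan gives no figure to reproduce. The check sets the sections side by side and then counts what could be affected.

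1. **Does summarized mean more than listed in this protocol?** Yes. The first rule in Protocol 9.3.1 says that collected data will be listed, and separately that descriptive methods will be used for safety and efficacy data. The categorical rule then specifies sample size, frequencies and percentages. A listing supplies none of these.

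2. **Does the SAP exclude a summary?** For categorical laboratory data, yes: the word only in SAP 17.1.2 leaves no room for one. For physical examination, SAP 17.2.1 plans a listing and nothing else. Weight is the exception, since SAP 17.1.4 summarizes it with vital signs.

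3. **Is the change declared?** No. SAP 3.4 covers biomarkers only.

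4. **Can another SAP rule bring categorical urinalysis back into a table?** Possibly. SAP 17.1.2.1 sends protocol parameters outside its Appendix 2 to the abnormality table if they have high/low/normal classes. SAP 17.1.2 cross-tabulates that table against baseline at each visit and at the worst case, with treatment-emergent counts. However, 17.1.2.1 defines the classes by comparing a value with the lower and upper limits of a normal range. It gives no mapping for ordinal results such as negative, trace or 1+. If such results are meant to enter the table, 17.1.2.1 conflicts with the listing-only rule in 17.1.2. If they are not, they have no table.

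5. **How many analytes are exposed?** Protocol Table 6 and SAP 17.1.2 name 10: specific gravity, pH, glucose, protein, blood, ketones, bilirubin, urobilinogen, nitrite and leukocyte esterase. Conditional microscopy is extra. Neither document says which are numeric or carry limits.
   - Assumption for the upper end: only specific gravity and pH are numeric, and none of the others has limits. Then 10 − 2 = 8 are listed only.
   - Lower end: all 10 are numeric or have limits. Then 0 are listed only.
   - Range: 0 to 8 of 10.

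6. **Do adverse events close the gap?** Not fully. Clinically significant laboratory changes are recorded as AEs and tabulated. Protocol 8.3.4 and Appendix 3 (10.3.1) exempt abnormalities associated with the underlying disease unless they are worse than expected for that participant. Changes that the investigator does not judge clinically significant are also left out.

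7. **Does the ESSDAI renal domain close it?** In part. Protocol Table 7 scores proteinuria, haematuria and renal function there, and Protocol 9.3.4 plans a summary of change in individual domains at weeks 24 and 48. The domain combines these features into one activity level and excludes renal involvement unrelated to the disease. It therefore does not report urine protein or urine blood separately, and it does not cover all causes.

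**The case against.** The strongest reply is that the consequence rests on something the documents do not state. They do not describe how the central laboratory reports urinalysis, and the Laboratory Manual is not part of them. SAP 17.1.2 says the laboratory supplies normal ranges, so some or all analytes may reach the abnormality cross-tabulations. The text of SAP Appendix 2 (toxicity grades) was not available for this check, so some urine items may be graded and shown as shifts. Clinically significant changes reach the AE tables, the renal domain captures disease activity, and serum creatinine is summarized as a continuous parameter. Physical examination is not in the primary endpoint: SAP 17.2 places it under other safety outcomes, and the examination is brief and symptom driven. The study tests no hypothesis, so no formal conclusion depends on these tables.

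Most of this stands as a limit on size. It does not remove the mismatch, which can be read from the text without any assumption, or the missing mapping for ordinal results.

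A reader might infer something stronger: that urinalysis goes almost entirely unsummarized, with 8 analytes × 5 scheduled post-baseline visits (weeks 16, 24, 36, 48 and safety follow-up) × 30 participants = 1,200 primary-endpoint results seen only in listings. The documents do not support that as a finding. It takes the upper end of the 0-to-8 range, full enrolment of a number given only as up to approximately 30, and no discontinuations. It is a ceiling on data points and does not measure any effect on a conclusion.

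**Conclusion.** The departure is real and undeclared: Protocol 9.3.1 requires summaries, including n and percentages for categorical variables, and SAP 17.1.2 and 17.2.1 provide listings. It should be corrected before database lock.

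For urinalysis, between 0 and 8 of the 10 named analytes would have no count, percentage or baseline shift. The upper end assumes that only specific gravity and pH are numeric, that the other eight have no high/low/normal limits, and that SAP Appendix 2 grades none of them. AE reporting and the ESSDAI renal domain reduce what could be missed but do not replace a per-analyte comparison with baseline.

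For physical examination, the issue is consistency with the protocol and does not touch the primary endpoint.

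**What to change.** - **SAP 17.1.2:** replace the listing-only sentence for categorical parameters. Categorical urinalysis results should be tabulated as n (%) at each analysis visit, with a shift table of baseline against the worst post-baseline category, overall and by parent-study arm.
- **SAP 17.1.2.1:** state how ordinal results map to the abnormality categories, and which urinalysis analytes are numeric or carry limits. This also removes the tension between 17.1.2 and 17.1.2.1.
- **SAP 17.2.1:** either add a count of participants with new or worsened examination abnormalities, or record the listing-only choice in SAP 3.4 with a reason.

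The cost is SAP wording and one or two small extra tables. The data are already collected, and SAP 6.3 already defines analysis visits for urinalysis.

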9.3.2. Primary Endpoint Analysis

Primary endpoint of long-term safety will be assessed through AEs, AESI, incidence of SAEs, changes in laboratory test results, vital signs, and ECG. Please refer the Section 8.3 for more details. Full details of the secondary analyses will be included in the SAP.

9.3.3. Secondary Endpoint(s) Analysis

The key secondary endpoints of CRESS, ESSDAI, clinESSDAI, ESSPRI, and STAR responders will be assessed at week 24 and week 48.

The proportion along with an exact 90% CI of CRESS, ESSDAI, clinESSDAI, ESSPRI, and STAR responders will be presented at week 24 and week 48.

[figure not shown]
Secondary endpoints of change from OLE baseline in ESSDAI, clinESSDAI, and ESSPRI scores will be summarized descriptively at week 24 and week 48. Observed data will also be summarized at OLE baseline, week 24 and week 48.

Plots of mean changes from the OLE baseline will be presented along with their 90% confidence intervals at each scheduled timepoint for ESSDAI, clinESSDAI, and ESSPRI. Box and Whisker plots will also be presented for the change from OLE baseline for each scheduled timepoint.

9.3.4. Exploratory Endpoints Analysis

To explore the effect of efgartigimod on clinical pSS, glandular measures and patient-reported outcomes, serum and blood biomarkers the following analysis will be performed:

- The proportion along with an exact 90% CI of adjusted CRESS (without serology item) will be presented at week 24 and week 48
- Change from OLE baseline in activity of individual ESSDAI domains score, Hocevar score, Schirmer's test score, OSS score, MFI score, physical component and mental component scores of SF-36, PGA score, individual ESSPRI score, EQ-5D-5L utilities score, VAS score will be summarized descriptively at week 24 and week 48. Observed data will also be summarized at OLE baseline, week 24 and week 48

- Percentage change from OLE baseline scores of SWSF, UWSF will be summarized descriptively at week 24 and week 48. Observed data will also be summarized at OLE baseline, week 24 and week 48
- Observed data for response in salivary gland function and tear gland function (CRESS) and PASS score will be summarized descriptively at OLE baseline, week 24 and week 48
- CCI

- Counts and percentages of number of subjects who are on Q2W and QW dosing regimen will be presented at each scheduled visit
- Counts and percentage of the number of subjects with different clinESSDAI scores will be presented by each scheduled visit and the subgroups
- Time from first infusion to revert to QW dosing regimen will be analyzed using a Kaplan-Meier (KM) method. Summary statistics will include the upper and lower quartiles of duration (days) with 95% confidence interval, median duration (days), 95% confidence interval for median duration (days). KM probability of staying on Q2W dosing regimen will also be presented

All the primary, secondary and exploratory analysis will be based on the FAS.

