
 To assess the PD effect of efgartigimod 	
 Values, changes from baseline, and percent reduction from baseline in total IgG levels in serum over the 48-week treatment period Values, changes from baseline, and percent reduction from baseline in autoantibodies in serum over the 48-week treatment period: 
 Anti-Ro/SS A Anti-La/SS B

 To assess the exposure to efgartigimod 	
 Efgartigimod serum concentrations over the 48-week treatment period

 To assess the immunogenicity of efgartigimod 	
 Incidence and prevalence of ADA against efgartigimod over the 48-week treatment period
Exploratory	

 To explore the effect of efgartigimod on additional clinical pSS measures 	
 Proportion of responders on 2 of 4 items of the adjusted CRESS (without serology item) at weeks 24 and 48 when compared to baseline Change from baseline in activity of individual ESSDAI domains at weeks 24 and 48

 To explore the effect of efgartigimod on glandular measures 	
 Change from baseline in: 
 SWSF rate at weeks 24 and 48 UWSF rate at weeks 24 and 48 Hocevar score at weeks 24 and 48 Schirmer's test at weeks 24 and 48 OSS at weeks 24 and 48 Response in salivary gland as defined in CRESS at weeks 24 and 48 when compared to baseline Response in tear gland as defined in CRESS at weeks 24 and 48 when compared to baseline

 To explore the effect of efgartigimod on patient-reported outcomes 	
 Change from baseline in: 
 Total MFI score at weeks 24 and 48 Physical component and mental component scores of SF-36 at weeks 24 and 48 PGA at weeks 24 and 48 Individual ESSPRI scores at weeks 24 and 48 EQ-5D-5L utilities and VAS scores at weeks 24 and 48 PASS at weeks 24 and 48 when compared to baseline

Objectives	Endpoints

 • CCI [REDACTED] 	
 • CCI [REDACTED] • Values, changes from baseline, and percent reduction from baseline in RF in serum over the 48-week treatment period

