8.2.1. CRESS

CRESS has been developed to assess treatment efficacy in participants with pSS. CRESS consists of the following items, with definitions of treatment response and lower disease:²

- Systemic disease activity: As measured with clinESSDAI (Section 8.2.3)
 - Response is defined as a score of < 5 points
- Patient-reported symptoms: As measured with ESSPRI (Section 8.2.5.1)
 - Response is defined as a decrease of ≥ 1 point or $\geq 15\%$ from baseline

- Tear gland function: as measured with Schirmer's test (Section 8.2.6.3) and OSS (Section 8.2.6.4)
 - If Schirmer's test is ≤ 5 mm at baseline (abnormal), a response is defined as an increase of at least 5 mm from baseline OR
 - If OSS is ≥ 3 points at baseline (abnormal), a response is defined as a decrease of at least 2 points from baseline OR
 - If both OSS and Schirmer's scores are normal at baseline, a response is defined as no change that results in an abnormal OSS or Schirmer's score
- Salivary gland function: As measured with UWSF (Section 8.2.6.2) and SGUS
 - UWSF: At least 25% increase in score, or if score is 0 mL/min at baseline, any increase from baseline OR
 - SGUS: At least 25% decrease in total Hocevar³ from baseline
- Serology: As measured with serum IgG and RF
 - RF: Decrease of at least 25% from baseline OR
 - IgG: Reduction of at least 10% from baseline

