6.8. Common Calculations

For quantitative measurements, change from baseline will be calculated as:

- Test Value at Visit X – Baseline Value

A percent change from baseline can be calculated as;

Percent change from baseline at Visit X = (actual value at Visit X -baseline value) *100/baseline value.

Copyright © 2009, 2010, 2012, 2016, 2018, 2019, 2021, 2024 IQVIA. All rights reserved. The contents of this document are confidential and proprietary to IQVIA Holdings Inc. and its subsidiaries. Unauthorized use, disclosure or reproduction is strictly prohibited.

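### Salivary flow is a change-from-baseline endpoint in Table 2, but protocol 9.3.4 summarises only percentage change, with no visible rule for a zero UWSF baseline

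*Protocol*

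**What the plan says.** Protocol section 3, Table 2, has an exploratory objective on glandular measures. Under the lead-in "Change from baseline in" it lists five measures, among them "SWSF rate at weeks 24 and 48" and "UWSF rate at weeks 24 and 48"; the other three are Hocevar score, Schirmer's test and OSS.

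Protocol 9.3.4 splits that list. Hocevar, Schirmer and OSS are summarised as change from OLE baseline. The two flow rates get their own bullet: "Percentage change from OLE baseline scores of SWSF, UWSF will be summarized descriptively at week 24 and week 48". The bullet adds: "Observed data will also be summarized at OLE baseline, week 24 and week 48". It gives no reason for the different treatment.

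The documents treat change and percentage change as different quantities. For IgG, Table 2 names both: "Values, changes from baseline, and percent reduction from baseline in total IgG levels in serum over the 48-week treatment period". SAP 6.8 gives each its own formula; the percentage one is "actual value at Visit X -baseline value) *100/baseline value", with no provision for a zero baseline.

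The CRESS definition in protocol 8.2.1 does provide for zero flow. For UWSF, response is: "At least 25% increase in score, or if score is 0 mL/min at baseline, any increase from baseline". STAR (protocol 8.2.4) has an equivalent rule, and SAP 13.1.1 and 13.1.6 repeat both.

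**The concern.** The quantity named as the endpoint is not the quantity that section 9.3.4 summarises. If the sentence is followed literally, no within-participant change in mL/min is tabulated for either flow rate, although Table 2 promises exactly that.

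The substitute also has two known weaknesses for a measure with a floor at zero. It has no value for a participant who starts at 0 mL/min, and it gives very large values to participants who start just above 0. The response definitions deal with the first weakness for UWSF; the visible text for the continuous summary does not. A participant whose UWSF goes from 0 to a measurable rate would count as a salivary responder in CRESS and have no entry in the percentage-change table.

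What is at stake is how an exploratory, descriptive result reads. The study tests no hypothesis (protocol 9.1), so no error rate or confirmatory claim is involved.

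**Working it through.** The documents state no expected salivary flow and no sample-size calculation, so there is no planned figure to reproduce. The check compares the texts and then applies the SAP 6.8 formulas to assumed values.

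**1. Texts side by side**

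| Measure | Table 2 | Protocol 9.3.4 |
|---|---|---|
| Hocevar, Schirmer, OSS | change | change, observed values |
| SWSF, UWSF | change | percentage change, observed values |

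SAP 3.4, which lists changes from the protocol analysis, mentions only the biomarker data.

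**2. Same gain, different baselines**

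Change = value − baseline. Percentage change = (value − baseline) × 100 / baseline. The gain of 0.04 mL/min and the baselines are assumptions. The one flow level the documents mark as low is UWSF of 0.1 mL/min or less, a classification item in Table 8.

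| Baseline (mL/min) | Change | Percentage change |
|---|---|---|
| 0 | +0.04 | undefined (division by 0) |
| 0.01 | +0.04 | 0.04/0.01 = +400% |
| 0.10 | +0.04 | 0.04/0.10 = +40% |
| 0.20 | +0.04 | 0.04/0.20 = +20% |

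**3. Influence of one low baseline**

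Assume 30 participants: 29 go from 0.20 to 0.22 (+0.02 mL/min, +10%) and one goes from 0.01 to 0.05 (+0.04 mL/min, +400%).

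- Mean percentage change = (29 × 10 + 400)/30 = 690/30 = 23.0%, against 10% without that participant.
- Median and quartiles of percentage change = 10%, with or without that participant.
- Mean absolute change = (29 × 0.02 + 0.04)/30 = 0.62/30 = 0.021 mL/min, against 0.020 without.

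The SE moves with the mean. With 29 identical values and one lying 390 points away, the SE is 390/30 = 13 percentage points, all of it due to one person. Identical values for the other 29 are a simplification to isolate the effect; real data would add ordinary spread.

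**4. How many participants could have no percentage value**

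The share with UWSF = 0 at OLE baseline is not given. For N = 30 (protocol 9.5, approximate) and an assumed share s, the expected number is 30 × s and the chance of at least one is 1 − (1 − s)^30.

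| s | Expected number | Chance of at least one |
|---|---|---|
| 5% | 1.5 | 79% |
| 10% | 3 | 96% |
| 20% | 6 | 99.9% |
| 30% | 9 | >99.9% |

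**The case against.** The strongest reply is that the governing text may be out of sight. Protocol section 9 leaves technical detail to the SAP, whose exploratory endpoint rows and exploratory efficacy sections are redacted. An absolute-change summary or a zero-baseline rule could be there. This stands: the point can be made only about the protocol text and the visible SAP 6.8.

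A reader might infer that the salivary-flow results leave out the participants with the worst gland function. The documents do not support that. Zero-baseline participants are missing from one summary only. They remain in the observed values at OLE baseline, week 24 and week 48, and in the CRESS and STAR salivary items, which have an explicit zero rule.

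A reader might also infer that a few near-zero baselines would determine the whole result. They can dominate the mean, SE and 90% CI. They do not dominate the median that protocol 9.3.1 requires or the quartiles that SAP 7.2 adds. Nor is the effect in mL/min lost entirely: if the same participants are seen at both visits, the difference in observed visit means equals the mean absolute change. What the observed values lack is the spread and interval of within-participant change, and exact matching when visits are missed.

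Three further inferences go too far:

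- The zero rule belongs to the response definitions of two composite instruments. It shows that zero flow is foreseen, not that any particular number is expected in this cohort.
- That rule covers UWSF. None is stated for SWSF, so for SWSF only the mismatch with Table 2 is established.
- The documents give no measurement error for salivary flow, so a large percentage cannot be attributed to noise.

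Finally, percentage change fits the 25% threshold in CRESS and STAR, so keeping it as an extra is reasonable. That does not explain leaving out the change that Table 2 names.

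**Conclusion.** The point holds in limited form. Table 2 and protocol 9.3.4 disagree on the summary measure for SWSF and UWSF, and both texts are unredacted. For UWSF, the visible formula gives no value at a zero baseline, and no visible rule covers that case.

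The size depends on assumptions. With a zero-flow share of 5% to 30% among about 30 participants, roughly 2 to 9 would have no percentage change. With the assumed flows above, a single low-baseline participant moves the mean percentage change from 10% to 23%, while the median stays at 10% and the mean absolute change moves from 0.020 to 0.021 mL/min. If nobody has a zero or very low baseline, only the mismatch with Table 2 remains.

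The severity is low: a worthwhile clarification of exploratory, descriptive output that bears on neither the safety objective nor the secondary endpoints.

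**What to change.** In protocol 9.3.4, move SWSF and UWSF into the bullet that summarises change from OLE baseline, in mL/min, so that it matches Table 2. Include every participant with both values, zero baselines among them. Make the same entry in the SAP if the redacted sections do not already have it.

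If percentage change is kept, label it supplementary, rely on median and quartiles, and report the number excluded for a zero baseline at each visit.

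The cost is one sentence and one table shell. No new data or visits are needed.

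If percentage change was the intended endpoint, Table 2 should say so and the SAP should state how a zero baseline is handled. That is the weaker option, because it leaves zero-baseline participants without a change value.
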